Study visits from Week 1 Day 1 to Week 2 Day 1 should be completed on the designated date [with an allowed "visit window" of +/- 1 day for Week 1 Day 1 and Week 2 Day 1]

Study visits from Week 4 to Week 12 should be completed every 4 weeks on the designated date [with an allowed "visit window" of +/- 2 day]

Study visits after Week 12 (from Week 24) to EOT should be completed every 12 weeks on the designated date [with an allowed "visit window" of +/- 7 days].

Safety follow-up should be completed 30 days from the last dose of study treatment [with an allowed "visit window" of +/- 7 days].

Visit at weeks 62, 74, 86, 98, 110 or 122 that is two weeks post dose escalation should be completed once after dose escalation on the designated date [with an allowed "visit window" of +/- 1 day].

A delayed visit will have no impact on the next planned visit. The next visit should be completed as scheduled in order to avoid accumulation of additional weeks.

Visit name	Category	Protocol Section	Screening Phase	Treatment Phase										EOT (week 144) /Early Discontinuation	Safety follow-up ¹³		
				Screening/ Baseline	Week 1 Day 1	Week 2 Day 1	Week 4	Week 8	Week 12	Week 24	Week 36	Week 48	Every 12 weeks up to week 132 (w60, w72, w84, w96, w108, w120, w132)			Week 62/74/86/98/ 110/122 for patient dose escalating	
Days (+/- X days)			Day -28 to -1	1 (+/- 1 day)	8 (+/- 1 day)	29 (+/- 2 days)	57 (+/- 2 days)	85 (+/- 2 days)	169 (+/- 7 days)	253 (+/- 7 days)	337 (+/- 7 days)	(+/- 7 days)	(+/- 1 day)	(+/- 7 days)	(+/- 7 days)		
Prior/concomitant medications	D	8.2	X	Continuous													
Physical Examinations	S	8.4	X	X		X	X	X	X	X	X	X		X			
Extra medullary Involvement	D		X														
ECOG Performance status	D	8.4.1	X	X		X	X	X	X	X	X	X		X			
Height	D	8.4	X														
Weight	D	8.4	X	X				X	X	X	X	X		X			
Vital signs ¹	D	8.4	X	X	X	X	X	X	X	X	X	X		X			
Laboratory assessments		8.4.2															
Hematology	D	8.4.2	X	X	X	X	X	X	X	X	X	X	X	X			
Chemistry ²	D	8.4.2	X	X	X	X	X	X	X	X	X	X	X	X			
Coagulation	D	8.4.2	X	As clinically indicated													

1. Blood Pressure reading to be taken in the supine position for all visits.
2. Hemoglobin A1c to be collected at screening only.

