1.1 Study design

The study is an international, multi-center, non-comparative, phase IIIb, treatment optimization study of asciminib (randomized 1:1 to either 40 mg b.i.d. or 80 mg q.d.) in adult subjects previously treated with 2 or more TKIs. 156 subjects will be randomized to either asciminib 40 mg b.i.d. or 80 mg q.d. An additional 30 subjects (randomized to either asciminib 40 mg b.i.d. or 80 mg q.d.) intolerant only to last TKI and in MMR at baseline will also be included.

Randomization is only used to have a balance in the allocation of treatment into either asciminib 40 mg b.i.d. or 80 mg q.d. The trial will not be powered to compare both treatments.

In subjects not achieving MMR at 48 weeks or losing the response after the week 48 assessment up to week 108, asciminib dose may be escalated to 200 mg q.d. if in the investigator's opinion

the subject may benefit from the escalation. In addition, there must not be any grade 3 or 4 toxicity while on therapy, or persistent grade 2 toxicity, possibly related to asciminib and unresponsive to optimal management.

[figure not shown]
BCR::ABL1 and **CCI** results are required before increasing asciminib dose, therefore the dose escalation can occur at next scheduled visit upon results review of the prior visit. In subjects losing response after the week 48 assessment, the last possible time point to initiate the 200 mg dose will be the week 120 visit to ensure that efficacy and safety of the dose escalation can be sufficiently established during the remaining trial follow up period.

If a dose decrease is required, subjects will return to the initial dosing regimen (q.d. or b.i.d.) they were using before the dose increase which was considered tolerable. For this reason, if a subject escalates from 40 mg b.i.d. to 200 mg q.d., in case of a required dose decrease, use of 80 mg q.d. is not allowed and the subject will continue 40 mg b.i.d. asciminib.

All subjects will be treated for a maximum duration of 144 weeks.

The primary endpoint of the study is MMR at 48 weeks.

Figure 1-1 Study design

*Treatment assignment to 40 mg b.i.d. or 80 mg q.d. (1:1) will be done through Interactive Response Technology (IRT).

Three analyses are planned for this study, including the 48-week primary analysis, the 96-week analysis, and the End-of-Study-Treatment (EOsT) analysis. The timing when those analyses are conducted is summarized in Section 2.1.

No formal interim efficacy analysis is planned in this study.

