1. ***pre-treatment period:*** from day of subject’s informed consent to the day before first administration of study treatment
2. ***on-treatment period:*** from date of first administration of study treatment to 30 days after date of last administration of study treatment (including start and stop date).
3. ***post-treatment period:*** starting at day 31 after last administration of study treatment.

If dates are incomplete in a way that clear assignment to pre-, on-, post-treatment period cannot be made, then the respective data will be assigned to the on-treatment period.

Safety summaries (tables, figures) on the corresponding Safety set include only data from the on-treatment period with the exception of baseline data which will also be summarized where appropriate (e.g. change from baseline summaries). In particular, summary tables for adverse events (AEs) will summarize only on-treatment events, with a start date during the on-treatment period. In addition, a separate summary for death will be provided.

However, all safety data (including those from the pre-treatment and post-treatment) will be listed and flagged as appropriate.

Efficacy summaries on the FAS and FAS 2 (apart from OS and PFS) include data from baseline up to either the last assessment on or before the End of Treatment (EoT) visit or before or on treatment failure, whichever is the earliest.

The efficacy assessments collected post-treatment failure or post-EoT visit are not included in any efficacy analyses (except for OS and PFS analyses). However, they will be listed and flagged as appropriate.

Windows for multiple assessments

Data such as molecular response, cytogenetic response collected over time (including unscheduled visits) will be summarized by scheduled time point. As subjects do not always adhere to the visit schedule, visits will be remapped according to visit windows defined in Tables 2-1 to Table 2-3 of this document to enable by-visit analysis. Only those protocol-defined visits will have the visit window defined. Each assessment (including the end of treatment assessment), either scheduled or unscheduled, will have a mapped visit assigned, as long as study day is available, according to the defined visit window up to the date with data included.

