For subjects in the FAS who have not experienced any MMR, the time will be censored as follows in the Kaplan-Meier analysis:

- If a subject does not achieve the specified response before the cut-off date for the analysis, censoring time will be the last molecular assessment (PCR) date on treatment prior to the cut-off date or the EoT visit, whichever comes first.
- If a subject discontinues study treatment prior to achieving a response for a reason other than disease progression or death, then the subject will be censored at the last molecular assessment (PCR) date on treatment prior to the cut-off date or the EoT visit, whichever comes first.
- If a subject discontinues study treatment prior to achieving a response due to progression or death, then the censoring time will be set to the longest follow-up time in the treatment group, that is, consider the response is impossible to reach.
- In case no on-treatment response assessment was performed, the subject will be censored at day 1.

The estimated cumulative incidence rates and 95% confidence intervals at 12, 24, 48, 72, 96 and 144 weeks will be presented. The cumulative incidence curve will be plotted.

Duration of MMR

Duration of MMR is defined in protocol Section 8.3.1.1 as the time from the date of first documented MMR to the earliest date of confirmed loss of MMR, progression to AP or BC, or CML-related death. The time will be censored at the last molecular assessment (PCR) date while on treatment for subjects who have not experienced any of the above events. The duration of MMR will be analyzed for the subjects in FAS who achieve MMR at any time.

Duration of MMR will be analyzed by K-M method and presented by K-M plots. The survival distribution of duration of MMR will be estimated using the Kaplan-Meier method, and Kaplan-Meier curves, medians and 95% confidence intervals [[Brookmeyer and Crowley 1982](#)] of the medians, along with the proportion of subjects who are still in MMR at 24, 48, 72, 96 and 144 weeks and the associated 95% confidence intervals, will be presented.

Duration of MR4 without loss of MMR will be analyzed in a similar fashion to the analysis of duration of MMR.

The additional subjects who were intolerant to the last TKI and were in MMR already at baseline will be assessed for the duration of MMR using FAS 2.

CCyR rates at time points

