Subjects in FAS will be categorized with counts and percentages provided for cytogenetic response at week 48 and EOT. Shift tables will also be employed to examine the changes in cytogenetic response category from baseline.

CCyR rates at Weeks 48 and EOT and the associated 95% confidence intervals based on the Clopper-Pearson method will be presented.

TTF, PFS and OS

For each endpoint the survival distribution will be estimated using the Kaplan-Meier method, and Kaplan-Meier curves, medians and 95% confidence intervals [[Brookmeyer and Crowley](#)

[1982](#)] of the medians, along with the proportion of subjects who have not experienced the respective events at 1, 2 and 3 years and the associated 95% confidence intervals, will be presented.

TTF: For subjects in the FAS who have not reached treatment failure, their TTFs will be censored at the time of their last study assessment (PCR, cytogenetic, hematologic or extramedullary) before the cut-off date.

PFS: For subjects who have not experienced an event (disease progression to AP/BC or death from any cause), their PFS times will be censored at the date of last study assessment (PCR, cytogenetic, hematologic or extramedullary) before the cut-off date.

OS: Subjects who are alive at the time of the analysis data cutoff date will be censored at the date of last contact (see [Section 2.1.1](#)) before the cut-off date.

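### On the planned schedule nobody is at risk at the 3-year landmark for time to treatment failure, or in the FAS at the 144-week landmark for duration of MMR

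*SAP*

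**What the plan says.** SAP 2.6.2 sets one landmark list for TTF, PFS and OS: "the proportion of subjects who have not experienced the respective events at 1, 2 and 3 years", each with a 95% confidence interval. For duration of MMR it asks for "the proportion of subjects who are still in MMR at 24, 48, 72, 96 and 144 weeks". Duration of MR4 without loss of MMR is to be analysed in a similar way.

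Other parts of the plan fix how long a patient can be observed for these endpoints:

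- **Treatment length.** SAP 1.1 states: "All subjects will be treated for a maximum duration of 144 weeks".
- **Data cut at EOT.** SAP 2.1.1 states: "The efficacy assessments collected post-treatment failure or post-EoT visit are not included in any efficacy analyses". Only OS and PFS are exempt.
- **TTF censoring.** For patients without treatment failure, "their TTFs will be censored at the time of their last study assessment (PCR, cytogenetic, hematologic or extramedullary) before the cut-off date" (SAP 2.6.2).
- **Duration of MMR.** The clock starts at the first documented MMR (SAP 2.6.1.1). For patients without an event, "The time will be censored at the last molecular assessment (PCR) date while on treatment" (SAP 2.6.2).
- **Visits.** Protocol Section 8 states: "Study visits after Week 12 (from Week 24) to EOT should be completed every 12 weeks on the designated date", with a window of 7 days either side. The protocol summary schedules no RQ-PCR at Week 1, 2, 4 or 8, so Week 12 is the first planned post-baseline sample.

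**The concern.** A Kaplan-Meier proportion needs patients under observation at the time it is read. Past the last observation it is defined only if the curve has already reached zero, which cannot happen if the patient with the longest follow-up is censored free of the event at EOT. The two longest landmarks appear to have been chosen without reference to the follow-up limits. Three years is longer than the treatment period that bounds TTF. The 144-week figure suits an endpoint timed from randomization, such as time to MMR, but duration of MMR starts at response.

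At stake are two tabulated secondary results. They would either be reported as not estimable or carry a label of 3 years or 144 weeks that no observation supports. The last part of real follow-up for both endpoints would also have no tabulated estimate.

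**Working it through.** **Inputs**

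- Target day for Week k is 7k + 1 (SAP 2.1.1). Week 144: 144 × 7 + 1 = 1009. Week 12: 12 × 7 + 1 = 85. Both match the SAP's time-window tables.
- Visit windows: ±2 days at Week 12 and ±7 days at EOT (Protocol Section 8).
- A year is 365.25 days and a month is 30.4375 days (SAP 2.1.1).
- Durations are end date − start date + 1 (SAP 2.6.1).
- Efficacy Day 1 is randomization. Screening may occupy the 28 days before Week 1 Day 1 (Protocol 8.1).

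**TTF at 3 years**

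- Landmark: 3 × 365.25 = 1095.75 days.
- EOT on target: Day 1009; 1009 / 30.4375 = 33.1 months. Shortfall 1095.75 − 1009 = 86.75 days.
- EOT at the end of its window: Day 1016; 1016 / 30.4375 = 33.4 months. Shortfall 79.75 days.
- If randomization preceded first dose by the full screening period: 1016 + 28 = Day 1044; 1044 / 30.4375 = 34.3 months. Shortfall 51.75 days.

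In all three cases nobody is at risk at 3 years.

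**Duration of MMR at 144 weeks, FAS**

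- Landmark: 144 × 7 = 1008 days after first MMR.
- Target days: (1009 − 85 + 1) / 7 = 925 / 7 = 132.1 weeks. Shortfall 83 days.
- Most favourable windows: (1016 − 83 + 1) / 7 = 934 / 7 = 133.4 weeks. Shortfall 74 days.
- If a sample at Week 8 (from Day 55) showed MMR: (1016 − 55 + 1) / 7 = 137.4 weeks. At Week 4 (from Day 27): (1016 − 27 + 1) / 7 = 141.4 weeks.
- Latest first-MMR day that gives 1008 days: 1009 + 1 − 1008 = Day 2, or 1016 + 1 − 1008 = Day 9.

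Reaching 144 weeks therefore needs an unscheduled sample in MMR within roughly the first 9 days.

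**Follow-up left without a tabulated estimate**

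- TTF: 2 years is 730.5 days; (1009 − 730.5) / 7 = about 40 weeks.
- Duration of MMR: 132.1 − 96 = about 36 weeks.

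**A reachable late time for duration**

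- First MMR at Week 24 (Day 169): (1009 − 169 + 1) / 7 = 841 / 7 = 120.1 weeks, on target days.

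**The case against.** The strongest reply is that little depends on these cells. SAP 2.6.2 rules out testing of secondary efficacy endpoints, the trial is non-comparative, and the likely result is an entry marked not estimable. No rule in the SAP carries the last value forward. This stands, and it limits the weight of the point. It does not make the requested estimates obtainable.

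Several stronger readings are tempting, and the documents do not support them:

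- **That the end of follow-up goes unreported.** Full Kaplan-Meier curves and medians are planned for both endpoints, and MMR, MR4 and MR4.5 rates are planned at Week 144. Only the late tabulated TTF and duration estimates are missing.
- **That follow-up of dose-escalated patients is lost.** Escalation for lost response requires confirmed loss of MMR (Protocol 6.1 and 6.6.2), which SAP 2.6.1.3 already counts as a TTF event. So is BCR::ABL1 above 1%, or no CCyR, at Week 48. A later TTF landmark would therefore say little about most escalated patients. They have their own MMR rates at Weeks 96 and 144 (SAP 2.5.6) and separate disposition and safety summaries.
- **That the same is shown for PFS and OS.** The last scheduled contact is about Day 1016 + 30 + 7 = 1053, also short of 3 years. But these endpoints are exempt from the EOT data cut, and later deaths or contacts could be recorded off schedule.
- **That a 144-week duration is impossible for everyone.** Unscheduled samples are allowed and are mapped into the analysis. FAS 2 patients are in MMR at baseline and could reach about 144 weeks if baseline counts as first MMR.

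**Conclusion.** The point holds for two requested estimates. On the planned schedule no patient is at risk for TTF at 3 years: follow-up ends 80 to 87 days earlier, or about 52 days earlier under the most generous gap between randomization and dosing. No FAS patient is at risk for duration of MMR at 144 weeks, where the maximum is 74 to 83 days short. Duration of MR4 inherits the same problem because it is analysed in the same way.

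The conclusion assumes that EOT visits keep to their window, that the SAP's exclusion of post-EOT efficacy data is applied to TTF, that FAS patients are not in MMR at baseline as planned, and that no unscheduled PCR shows MMR in roughly the first 9 days.

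This is an error in the landmark lists of descriptive secondary tables. It should be corrected, but it does not touch the primary test or the definition of any endpoint.

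**What to change.** In SAP 2.6.2:

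- **TTF.** Give it its own list, separate from PFS and OS: 1 year, 2 years and Week 144. Read Week 144 at Day 1009 or at the last time with an adequate number at risk, and define adequate in advance. Patients whose EOT visit falls early in its window are censored before Day 1009.
- **Duration of MMR and of MR4, FAS.** Replace 144 weeks with a reachable time such as 120 weeks. For MMR, patients first in response by Week 24 can reach it on target days, but only narrowly: 120 weeks is 840 days and the target-day maximum for a Week 24 responder is 841.
- **FAS 2.** Keep 144 weeks for duration of MMR only if the SAP states that baseline counts as first MMR.
- **All landmarks.** Print the number at risk beside each estimate.

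The PFS and OS list should not change as a side effect. The cost is a split time list and a shorter longest horizon for two endpoints. No data collection, derivation or endpoint definition changes, apart from the FAS 2 clarification if 144 weeks is kept there.

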CCyR rates at Weeks 48 and EOT and the associated 95% confidence intervals based on the Pearson-Clopper method will be presented.

Treatment failure, disease progression and survival

Progression-Free-Survival (PFS) is defined as the time from the date of randomization to the earliest occurrence of documented disease progression to AP/BC or the date of death from any cause before the cut-off date.

The time will be censored at the date of last study assessment (PCR, cytogenetic, hematologic or extramedullary) or last post-treatment follow-up for patients without event.

Overall survival (OS) is defined as the time from the date of randomization to the date of death. Patients who are alive at the time of the analysis data cutoff date will be censored at the date of last contact before the cut-off date.

Time to treatment failure (TTF) is defined as the time from date of randomization to an event of treatment failure define as BCR-ABL1 > 1% IS. The following events will constitute 'treatment failure', and are based on the ELN criteria 2020 defining failure of a second line treatment adapted to include discontinuation of randomized treatment as an event:

- Twelve months (48 weeks) after the initiation of treatment BCR-ABL1 >1% IS
- Emergence of resistance mutations, high-risk ACA

For patients who have not reached treatment failure, their TTFs will be censored at the time of last study assessment (PCR, cytogenetic, hematologic or extramedullary) before the cut-off date.

TTF, PFS and OS will be estimated and graphically displayed using the K-M approach on FAS. The estimated rates by K-M method at various time points will be provided.

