2.6.1.3 Other secondary efficacy endpoints

Time to treatment failure (TTF) is defined as the time from date of randomization to an event of treatment failure define as BCR::ABL1 > 1% IS. The following events will constitute ‘treatment failure’ for analysis purpose, and are based on the ELN criteria 2020 defining failure of a second line treatment adapted to include discontinuation of randomized treatment as an event:

- BCR::ABL1 >1% IS at 48 weeks after initiation of therapy or no complete cytogenetic response at 48 weeks.
- Subject demonstrates new T315I mutation
- Subject shows lack or loss of response such as “Loss of CHR, CCyR or PCyR at any time after initiation of therapy OR confirmed loss of MMR”
- Progression to AP/BC

For subjects who have not reached treatment failure, their TTFs will be censored at the time of last study assessment (PCR, cytogenetic, hematologic or extramedullary) before the cut-off date.

TTF (in months) is calculated as: (date of treatment failure or censoring date (see [Section 2.6.2](#)) - date of randomization + 1)/30.4375.

Progression-Free-Survival (PFS) is defined as the time from the date of randomization to the earliest occurrence of documented disease progression to AP/BC or the date of death from any cause before the cut-off date. The time will be censored at the date of last study assessment (PCR, cytogenetic, hematologic or extramedullary) or last post-treatment follow-up for subjects without event.

PFS (in months) is calculated as: (date of disease progression/death or censoring date (see [Section 2.6.2](#)) - date of randomization + 1)/30.4375.

Overall survival (OS) is defined as the time from the date of randomization to the date of death. Subjects who are alive at the time of the analysis data cutoff date will be censored at the date of last contact (see [Section 2.1.1](#)) before the cut-off date. OS (in months) is calculated as: (date of death or censoring date (see [Section 2.6.2](#)) - date of randomization + 1)/30.4375.

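### SAP 2.6.2 gives a PFS censoring rule that conflicts with SAP 2.6.1.3 and the protocol, and its Kaplan-Meier curve can only be equal to or lower than theirs

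*SAP*

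**What the plan says.** **Censoring, rule A.** SAP 2.6.2 (TTF, PFS and OS) states that for event-free subjects "their PFS times will be censored at the date of last study assessment (PCR, cytogenetic, hematologic or extramedullary) before the cut-off date".

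**Censoring, rule B.** SAP 2.6.1.3 names the same four assessments and then adds "or last post-treatment follow-up for subjects without event". Protocol 12.5.1 does the same: "or last post-treatment follow-up for patients without event".

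**Cross-reference.** The computing formula in SAP 2.6.1.3 ("PFS (in months) is calculated as: (date of disease progression/death or censoring date") refers the reader to 2.6.2 for the censoring date. Code written from that formula would therefore follow rule A, although the paragraph just above it states rule B.

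**Events.** SAP 2.6.1.3 counts "the earliest occurrence of documented disease progression to AP/BC or the date of death from any cause before the cut-off date", with no limit to the on-treatment period. SAP 2.1.1 removes efficacy assessments made after treatment failure or after the end-of-treatment visit, but "except for OS and PFS analyses". SAP 2.7 plans a summary that includes post-treatment deaths.

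**Status.** SAP section 4 lists no change to protocol-specified analyses, so rule A is not a declared departure.

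**The concern.** One variable has two censoring rules in current text, and the programming reference leads to the one that departs from the protocol.

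The difference matters because rule A treats deaths and survivors differently. Under protocol Table 8-2 the molecular samples end at end of treatment. The minimum data that protocol 9.1.1 asks for after discontinuation (new treatments, adverse events) include none of the four assessments named in rule A. A discontinued subject who later dies stays at risk until the death and counts as an event. A discontinued subject known to be alive on the same day is normally censored back near the end-of-treatment visit. Time at risk then depends on the outcome. At stake are the PFS estimates at 1, 2 and 3 years that SAP 2.6.2 asks for.

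**Working it through.** The documents state no PFS rate, event count or power, so there is no figure to reproduce.

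**1. Direction.** The Kaplan-Meier estimate is S(t) = Π(1 − d/n) over event times up to t. Both rules have the same events d. Rule A never censors later than rule B, so its n is never larger. Each factor is equal or smaller, and so is S(t). This needs no assumption about rates.

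**2. Inputs for size**
- Sample size 156 (protocol 12.8.1); maximum treatment 144 weeks, or 1,008 days (protocol section 3).
- Discontinuation 37.6% (protocol 1.1 and 4.2, earlier phase III trial, asciminib arm). *Assumption:* this was reached at 14.9 months, which protocol 1.1 gives only as the median follow-up.
- *Assumption:* event rate 1% per year on treatment and 1% to 4% per year off treatment. The documents give no such rates.
- Post-treatment contact: 30 days is scheduled (protocol Table 8-1). Anything longer is an assumption.

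The discontinuation hazard is −ln(1 − 0.376)/14.9 = 0.4716/14.9 = 0.03165 per month. Since 1,008 days is 33.12 months, the share completing treatment is exp(−0.03165 × 33.12) = 0.351, or about 55 of 156.

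**3. PFS at 2 years, rule A minus rule B (simulation, percentage points)**

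| Contact after treatment | 1%/yr off treatment | 4%/yr off treatment |
|---|---|---|
| 30 days | −0.1 | −0.1 |
| 26 weeks | −0.4 | −0.5 |
| to study end | −1.0 | −1.9 |

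With one year of contact at 4% per year the gap is 1.2 points. The standard error at n = 156 is about 1.5 points. More extreme assumptions (6% per year off-treatment death plus 2% per year progression, contact to study end) give 3.2 points. At 1 year the gap was 0.0 to 0.6 points in every scenario.

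**4. PFS at 3 years.** Three years is day 1,096. The week 144 target is day 144 × 7 + 1 = 1,009, and the 30-day follow-up ends near day 1,039. Under rule A, event-free completers are censored at about day 1,009. If one then dies inside the 30 days and no later assessments exist, the risk set is that subject alone. The factor is 1 − 1/1 = 0 and the curve falls to zero. Under rule B about 55 subjects are still at risk and the factor is 1 − 1/55 = 0.982.

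The expected number of such deaths is 54.7 × rate × 30/365.25:
- at 1% per year, 0.045, so P(at least one) = 1 − exp(−0.045) = 4.4%
- at 4% per year, 0.180, so P(at least one) = 1 − exp(−0.180) = 16%

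Simulation agrees. The 3-year estimate was below 50% in about 3% to 16% of trials under rule A, depending on the assumed rate and the spread of end-of-treatment visits, and in none under rule B. With 30-day contact only, nobody is observed at day 1,096 under either rule: the maximum is (1,008 + 30)/365.25 = 2.84 years.

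**5. Against the true PFS at 2 years**

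| Scenario | True | Rule A | Rule B |
|---|---|---|---|
| 1%/yr death on and off treatment, contact to study end | 98.0% | 97.0% | 98.0% |
| 6%/yr off-treatment death, 30-day contact | 95.2% | 97.6% | 97.7% |
| 1%/yr death, 2%/yr progression, contact to study end, progression unseen off treatment | 94.2% | 93.3% | 95.3% |

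Rule A can lie below or above the truth, and rule B is not free of error.

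**The case against.** The strongest reply is that the schedule makes the difference trivial. The only contact planned after end of treatment is the 30-day safety visit or call. Protocol 9.1.1 sets no duration for further contact. It asks for telephone contact when a participant cannot or will not attend visits, and only preferably on the visit schedule. After 30 days, protocol 10.1.4 limits serious adverse event reporting to events suspected to be related to treatment, so late deaths may not be captured systematically. This stands: for the 1- and 2-year estimates, 30 days of contact gives a gap of about 0.1 point or less.

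It can also be said that rule A does not always stop at end of treatment. It includes blood counts, and protocol 6.6.4 requires follow-up of clinically significant laboratory values after some discontinuations. That stands too. Survivors are censored earlier, not removed, and any later named assessment extends their time at risk.

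Finally, censoring at the last disease assessment is a respectable choice, because a telephone call does not assess progression to accelerated phase or blast crisis. That would justify rule A only if deaths beyond the last assessment were also excluded, and the SAP keeps them. It does not justify two rules for one variable, and it does not protect the 3-year estimate.

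**Conclusion.** The conflict is real, current and undeclared. On the same data the 2.6.2 rule gives a PFS curve equal to or below the one under the protocol and SAP 2.6.1.3.

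Relative to the protocol rule, the 2-year gap is about 0.1 point with the scheduled 30-day follow-up. It is about 1 to 2 points only if contact and death ascertainment continue to study end. Those sizes rest on assumed off-treatment rates of 1% to 4% per year and on pairing 37.6% discontinuation with 14.9 months; the documents give neither. The 3-year estimate is the exposed one, since a single death soon after week 144 can drive it towards zero even with 30-day contact.

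A reader might infer that rule A biases PFS downward in general. The documents do not support that. The downward shift is certain only against the protocol rule; the direction against the true PFS depends on how long deaths are ascertained. Nor do they support the inference that 9.1.1 guarantees long contact.

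PFS is secondary, descriptive and untested, so the week 48 primary analysis is untouched. The text should still be corrected before PFS is programmed.

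**What to change.** Replace the PFS sentence in SAP 2.6.2 with the rule in SAP 2.6.1.3 and protocol 12.5.1, made explicit: subjects without an event are censored at the later of the last study assessment and the last post-treatment follow-up, on or before the cut-off.

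Define last post-treatment follow-up (which contacts qualify and for how long) so that deaths and survivors after the last assessment are followed to the same point. Use the same wording in 2.6.1.3, where the present text does not say which of the two dates applies.

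State the downside: a telephone contact does not assess accelerated phase or blast crisis, so unseen progression may slightly overstate PFS. Add a sensitivity analysis that stops both events and time at risk at the last disease assessment, to show the effect.

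The cost is a few sentences in the SAP, one censoring variable and one extra table. SAP 2.1.1 already derives last contact dates for overall survival, so no new data are needed.
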